7.3.4 Final Study Visits

CTSI visit 2 (Days 78-84)

- Record adverse events as reported by participant or observed by investigator.
- *Measure weight, waist, and blood pressure*
- Complete end of treatment surveys: ASA24 hour dietary recall; International Physical Activity Questionnaire; Pittsburgh Sleep Quality Index; PROMIS-Depression 6a, medical history update, and medication history update.
- Provide participants with instructions for the at-home assessments including wrist accelerometry and continuous glucose monitoring.

Week 12 (Days 78-84)

- Record adverse events as reported by participant or observed by investigator.

CONFIDENTIAL

- Participant will wear the continuous glucose monitor for 7 days 24/7. Return the continuous glucose monitor to the study team in the prepaid package after day 92.
- Record results of continuous glucose monitor.
- Participant will wear wrist accelerometer (24/7).
- Complete Sleep Diaries (daily), SRM-5 (daily), and Epworth Sleepiness Scale (day 83)

Week 13 (Days 85-91)

- Record adverse events as reported by participant or observed by investigator.
- Complete Sleep Diaries (daily), SRM-5 (daily), and Epworth Sleepiness Scale (day 90)
- Participant to ship wrist accelerometer back to the study team in the prepaid package after 14 nights of wear time (day 92).
- Record results of wrist accelerometer.

Final Visit (optional)

Study team will review baseline and end of treatment continuous glucose monitoring reports, wrist accelerometer, weight measurements, and ASA24 reports with participants who are interested in this optional final visit.

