7.3.2 Enrollment/Baseline

Enrollment/Baseline CTSI Visit 1 (Visit 1, Day 0)

- Obtain written informed consent and written audio consent of the potential participant verified by signature on study informed consent form.
- Verify inclusion/exclusion criteria.
- Review medical history to determine eligibility based on inclusion/exclusion criteria (prediabetes diagnosis, most recent HbA1c \geq 5.7% and $<$ 6.5%, no diagnosis of current or previous bipolar disorder).
- Obtain demographic information, medical history, medication history, and alcohol use history.
- Record vital signs, results of examinations, other assessments.
- HbA1c point of care fingerstick (if needed) and blood draw for future analyses (optional).
- Provide eligible participants with instructions for the at-home assessments with wrist accelerometry, continuous glucose monitoring, pulse oximetry (if needed), and baseline surveys via REDCap including daily sleep diaries.

CONFIDENTIAL

This material is the property of the NYU School of Medicine and NYU Langone Health. Do not disclose or use except as authorized in writing by the study sponsor
Behavioral Intervention Template Version: 11 January 2019

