7.3.3 Intermediate Visits

7.3.3.1 At-home visits

Week 1 (Days 1 - 7)

- Record adverse events as reported by participant or observed by investigator.
- Participant will wear the continuous glucose monitor for 7 days 24/7. Return the continuous glucose monitor to the study team in the prepaid package after day 14.
- If needed, participant will wear the pulse oximeter for 1 night. Return the pulse oximeter to the study team in the prepaid package after 1 night of wear time.
- Record results of continuous glucose monitor and pulse oximeter.
- Participant will wear wrist accelerometer (24/7).
- Complete Sleep Diaries (daily), SRM-5 (daily), and Epworth Sleepiness Scale (day 6)
- Complete baseline surveys: ASA24 hour dietary recall; Composite Scale of Morningness; International Physical Activity Questionnaire; Pittsburgh Sleep Quality Index; PROMIS-Depression 6a; Sleep Environment Survey.
- Record participant's adherence to intervention program.

Week 2 (Days 8 - 14)

- Record adverse events as reported by participant or observed by investigator.
- Record results of wrist accelerometer.
- Complete Sleep Diaries (daily), SRM-5 (daily) and Epworth Sleepiness Scale (day 13).
- Record participant's adherence to intervention program.

Week 3 (Days 15-21)

- Participant to ship wrist accelerometer back to the study team in the prepaid package after 14 nights of wear time (day 15).
- Record adverse events as reported by participant or observed by investigator.
- Determine eligibility for intervention based on wrist accelerometry and pulse oximetry data.
- Randomize eligible participants to sleep intervention or control arm.
- Notify participant of eligibility and arrange for weekly videoconference intervention sessions.

Weeks 4-11 (Days 22 – 77)

- Record adverse events as reported by participant or observed by investigator.
- Record results of daily Sleep Diary and weekly Epworth Sleepiness Scale results.
- Administer the study intervention to the participant in accordance with the intervention manual for the sleep intervention arm or the control arm.
- Record participant's adherence to intervention program.

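### Do the two printed day ranges for the end-of-treatment CGM leave the primary endpoint's follow-up measurement undefined?

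*Protocol*

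**What the plan says.** Section 7.3.4 gives two entries the same days: the visit, "CTSI visit 2 (Days 78-84", and the CGM week, "Week 12 (Days 78-84". It also prints fixed days for related tasks: a sleepiness survey ("and Epworth Sleepiness Scale (day 83"), accelerometer shipping ("in the prepaid package after 14 nights of wear time (day 92") and the monitor's return ("Return the continuous glucose monitor to the study team in the prepaid package after day 92"). The intervention in Section 7.3.3.1 occupies days 22-77. The Schematic repeats that period and the Visit 2 window, and gives one combined block, days 78-91, for the end-of-study devices.

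The baseline block has the same shape. It opens with "Enrollment/Baseline CTSI Visit 1 (Visit 1, Day 0", followed by CGM on days 1-7, a survey ("and Epworth Sleepiness Scale (day 6") and shipping ("in the prepaid package after 14 nights of wear time (day 15").

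Attachment A, the tabular Schedule of Events, prints other days: intervention 24-80, Visit 2 on 81-87, and the second CGM mark under Week 13, days 88-95. Section 19 says that attachments are relevant to the protocol but not part of it.

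Three other places bear on when the sensor goes on. Section 5.5 has participants come back to the CTSI for the monitor once the 8-week intervention is over. Section 2.3.1 has a trained team member insert the sensor. Section 4.2.1 bases the primary endpoint on seven days of CGM and names no study days. The SAP text supplied (1.3.2) models change from baseline and sets no follow-up window.

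**The concern.** The follow-up CGM supplies half of every participant's primary outcome, and Section 3.1 states the hypothesis for the end of 8 weeks of treatment. Two non-overlapping day ranges suggest two designs: glucose measured straight after treatment, or more than a week later. If an effect on glucose faded quickly, a later measurement would dilute it.

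Section 7.3.4 also seems not to fit its own visit window. Wear cannot start before staff place the sensor, and the visit may fall on any of seven days. A seven-day wear period therefore cannot stay inside the same seven days except in one case. An analyst who took the heading as a strict window would discard valid primary-endpoint data from most participants.

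**Working it through.** **Inputs.** Section 7.3: intervention ends day 77, Visit 2 on days 78-84, CGM heading days 78-84. Attachment A: intervention ends day 80, Visit 2 on days 81-87, CGM heading days 88-95. Wear lasts 7 days.

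**1. Reproduce the printed weeks.** With 7-day weeks, week w covers days 7(w-1)+1 to 7w. Week 12 is 7×11+1 = 78 to 84 and Week 13 is 85 to 91, as Section 7.3.4 prints. Attachment A does not follow this rule. Week 2 (days 8-15) and Week 3 (days 16-23) each span 8 days, and Weeks 4-11 (days 24-80) span 80-24+1 = 57 days instead of 56. That adds 1+1+1 = 3 days, which moves the start of Visit 2 from day 78 to day 81. Attachment A then gives Visit 2 its own week before the CGM column, adding 7. Together 3+7 = 10 = 88-78, the whole gap between the two printed starts.

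**2. Project wear from each allowed visit day v.** A visit-day start gives wear v to v+6. A next-day start, which is the baseline pattern, gives v+1 to v+7.

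| Calendar | Start | First wear day | Last wear day | Visits fitting the heading | Days from end of intervention to first wear day |
|---|---|---|---|---|---|
| Section 7.3 | visit day | 78-84 | 84-90 | 1 of 7 (v=78) | 1-7 |
| Section 7.3 | next day | 79-85 | 85-91 | 0 of 7 | 2-8 |
| Attachment A | visit day | 81-87 | 87-93 | 0 of 7 | 1-7 |
| Attachment A | next day | 82-88 | 88-94 | 1 of 7 (v=87) | 2-8 |

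The last column is the one that matters for the endpoint, and it is the same in both calendars. The headline contrast, 78-77 = 1 day against 88-80 = 8 days, appears only if wear starts on the first day of each heading regardless of the visit. In Attachment A that would separate sensor placement from Visit 2, and no further staff contact is scheduled for it. Section 7.3.6 allows an unscheduled visit only to replace a monitor.

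**3. Are the headings exclusion windows?** No passage says so. The follow-up days for wear, surveys and shipping equal the baseline days plus 77: 1 to 78, 6 to 83, 7 to 84, 13 to 90, 15 to 92. The same shift would put the visit on day 0+77 = 77, which is not an allowed day. The likely explanation, which is my inference, is that the baseline block was copied forward as a nominal calendar. The monitor's return line suits every allowed visit, since the latest wear day is 91.

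**4. Related fixed days.** Fourteen accelerometer nights from a visit-day start end on day v+14, that is 92 (v=78) to 98 (v=84). The printed 92 is the earliest case, and the 14-night requirement stands beside it. The day-83 survey is part of a weekly REDCap series that already runs through Weeks 4-11. It needs neither a device nor a visit, so falling one day before a day-84 visit is no conflict.

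**5. Interval from the last session.** Assume session 8 falls on any of the last 7 intervention days. The shortest interval to CGM start is 78-77 = 1 or 81-80 = 1 day, and the longest is 84-71 = 13 or 87-74 = 13. The range is 1-13 days in both calendars, or 2-14 with a next-day start.

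**The case for a change.** The strongest case for acting has three parts. First, Attachment A is the only tabular schedule and is what a coordinator would keep at hand, so placing it outside the protocol does not make it harmless. Second, the misfit between wear and visit window lies wholly inside Section 7.3.4 and survives without Attachment A. Third, the stated participation of about 15 weeks seems nearer to Attachment A's last day (103/7 = 14.7 weeks) than to the body's last printed wear day (91/7 = 13.0 weeks).

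The facts in this stand: the day numbers disagree, the fit counts are right, and no sentence says the headings are nominal. The consequence does not stand. Staff cannot start wear before inserting the sensor, and participants come to Visit 2 to get it, so both calendars lead to the same act at the same point after treatment. The duration argument is weak: with a day-84 visit the body calendar runs to day 98, or 98/7 = 14.0 weeks. Nor does the analyst need a study-day window, since Section 4.2.1 asks for seven days of CGM and the sensor record shows when they began.

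Reporting the session-to-CGM interval by arm would be a reasonable description of conduct, but the primary analysis does not depend on it.

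**Conclusion.** The printed days conflict, but the measurement is sufficiently defined. This is a clerical slip combined with a gap that staff and analysts fill sensibly. Followed as written, the plan yields seven days of CGM starting 1-7 days after the intervention period (2-8 with a next-day start) under either calendar and on the same schedule in both arms. There is no route to a between-arm bias. The documents give no evidence that an effect fades over these days, and no loss of power can be computed.

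This rests on two readings: the sensor is placed at Visit 2 (Sections 2.3.1 and 5.5), and the week headings are nominal rather than exclusion rules. The SAP's account of the analysis is largely in the past tense, so renumbering would probably come after the data were collected and could not alter which days were measured. Aligning the day numbers at a later edit would be good housekeeping, but it would change neither the endpoint, the analysis nor the result.

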7.3.5 Withdrawal Visit

If a participant withdraws or is withdrawn from the study, no further study visits or procedures will be completed.

7.3.6 Unscheduled Visit

If a participant needs an unscheduled visit for replacing the continuous glucose monitor, this visit will be arranged by the project coordinator and documented in REDCap.

7.4 Concomitant Medications, Treatments, and Procedures

All concomitant prescription medications taken during study participation will be recorded on the case report forms (CRFs). For this protocol, a prescription medication is defined as a medication that can be prescribed only by a properly authorized/licensed clinician. Medications to be reported in the CRF are concomitant prescription medications, over-the-counter medications and non-prescription medications.

7.5 Justification for Sensitive Procedures

Not applicable.

7.5.1 Precautionary Medications, Treatments, and Procedures

Not applicable.

7.6 Prohibited Medications, Treatments, and Procedures

Not applicable.

7.7 Prophylactic Medications, Treatments, and Procedures

Not applicable.

7.8 Participant Access to Study Intervention at Study Closure

Not applicable.

CONFIDENTIAL

This material is the property of the NYU School of Medicine and NYU Langone Health. Do not disclose or use except as authorized in writing by the study sponsor
Behavioral Intervention Template Version: 11 January 2019

8 Assessment of Safety

8.1 Specification of Safety Parameters

The study will involve no more than minimal risk to research participants. The probability and magnitude of harm or discomfort anticipated for this research are not greater than what this same population encounters in daily life or during the performance of physical or psychological examinations or tests. The only alternative to study participation is non-participation.

8.1.1 Definition of Adverse Events (AE)

An **adverse event** (AE) is any symptom, sign, illness or experience that develops or worsens in severity during the course of the study. Intercurrent illnesses or injuries should be regarded as adverse events. Abnormal results of diagnostic procedures are considered to be adverse events if the abnormality:

- results in study withdrawal
- is associated with a serious adverse event
- is associated with clinical signs or symptoms
- leads to additional treatment or to further diagnostic tests
- is considered by the investigator to be of clinical significance

8.1.2 Definition of Serious Adverse Events (SAE)

Serious Adverse Event

Adverse events are classified as serious or non-serious. A **serious adverse event** is any AE that is:

- fatal
- life-threatening
- requires or prolongs hospital stay
- results in persistent or significant disability or incapacity
- a congenital anomaly or birth defect
- an important medical event

Important medical events are those that may not be immediately life threatening, but are clearly of major clinical significance. They may jeopardize the subject, and may require intervention to prevent one of the other serious outcomes noted above. For example, drug overdose or abuse, a seizure that did not result in in-patient hospitalization, or intensive treatment of bronchospasm in an emergency department would typically be considered serious.

All adverse events that do not meet any of the criteria for serious should be regarded as **non-serious adverse events**.

8.1.3 Definition of Unanticipated Problems (UP)

Unanticipated Problems Involving Risk to Subjects or Others

Any incident, experience, or outcome that meets all of the following criteria:

- Unexpected in nature, severity, or frequency (i.e. not described in study-related documents such as the IRB-approved protocol or consent form, the investigators brochure, etc)
- Related or possibly related to participation in the research (i.e. possibly related means there is a reasonable possibility that the incident experience, or outcome may have been caused by the procedures involved in the research)
- Suggests that the research places subjects or others at greater risk of harm (including physical, psychological, economic, or social harm).

CONFIDENTIAL

This material is the property of the NYU School of Medicine and NYU Langone Health. Do not disclose or use except as authorized in writing by the study sponsor
Behavioral Intervention Template Version: 11 January 2019

8.2 Classification of an Adverse Event

8.2.1 Severity of Event

For AEs not included in the protocol defined grading system, the following guidelines will be used to describe severity.

- **Mild** – Events require minimal or no treatment and do not interfere with the participant's daily activities.
- **Moderate** – Events result in a low level of inconvenience or concern with the therapeutic measures. Moderate events may cause some interference with functioning.
- **Severe** – Events interrupt a participant's usual daily activity and may require systemic drug therapy or other treatment. Severe events are usually potentially life-threatening or incapacitating.

8.2.2 Relationship to Study Intervention

For all collected AEs, the clinician who examines and evaluates the participant will determine the AE's causality based on temporal relationship and his/her clinical judgment. The degree of certainty about causality will be graded using the categories below.

- **Definitely Related** – *There is clear evidence to suggest a causal relationship, and other possible contributing factors can be ruled out. The clinical event, including an abnormal laboratory test result, occurs in a plausible time relationship to intervention administration and cannot be explained by concurrent disease or other drugs or chemicals. The response to withdrawal of the intervention (dechallenge) should be clinically plausible.*
- **Probably Related** – *There is evidence to suggest a causal relationship, and the influence of other factors is unlikely. The clinical event, including an abnormal laboratory test result, occurs within a reasonable time after administration of the intervention, is unlikely to be attributed to concurrent disease or other drugs or chemicals, and follows a clinically reasonable response on withdrawal (dechallenge). Rechallenge information is not required to fulfill this definition.*
- **Possibly Related** – *There is some evidence to suggest a causal relationship (e.g., the event occurred within a reasonable time after administration of the trial intervention). However, other factors may have contributed to the event (e.g., the participant's clinical condition, other concomitant events). Although an AE may rate only as "possibly related" soon after discovery, it can be flagged as requiring more information and later be upgraded to "probably related" or "definitely related," as appropriate.*
- **Unlikely to be related** – *A clinical event, including an abnormal laboratory test result, whose temporal relationship to intervention administration makes a causal relationship improbable (e.g., the event did not occur within a reasonable time after administration of the trial intervention) and in which other drugs or chemicals or underlying disease provides plausible explanations (e.g., the participant's clinical condition, other concomitant treatments).*
- **Not Related** – *The AE is completely independent of study intervention administration, and/or evidence exists that the event is definitely related to another etiology. There must be an alternative, definitive etiology documented by the clinician.*

8.2.3 Expectedness

[name], PI will be responsible for determining whether an AE is expected or unexpected. An AE will be considered unexpected if the nature, severity, or frequency of the event is not consistent with the risk information previously described for the study intervention.

8.3 Time Period and Frequency for Event Assessment and Follow-Up

The occurrence of an AE or SAE may come to the attention of study personnel during study visits and interviews of a study participant presenting for medical care, or upon review by a study monitor. All AEs including local and systemic reactions not meeting the criteria for SAEs will be captured on the

CONFIDENTIAL

This material is the property of the NYU School of Medicine and NYU Langone Health. Do not disclose or use except as authorized in writing by the study sponsor
Behavioral Intervention Template Version: 11 January 2019

appropriate RF. Information to be collected includes event description, time of onset, clinician's assessment of severity, relationship to study intervention (assessed only by those with the training and authority to make a diagnosis), and time of resolution/stabilization of the event. All AEs occurring while on study must be documented appropriately regardless of relationship. All AEs will be followed to adequate resolution.

Any medical condition that is present at the time that the participant is screened will be considered as baseline and not reported as an AE. However, if the study participant's condition deteriorates at any time during the study, it will be recorded as an AE. UPs will be recorded in the data collection system throughout the study.

Changes in the severity of an AE will be documented to allow an assessment of the duration of the event at each level of severity to be performed. AEs characterized as intermittent require documentation of onset and duration of each episode.

The PI will record all reportable events with start dates occurring any time after informed consent is obtained until 7 (for non-serious AEs) or 30 days (for SAEs) after the last day of study participation. At each study visit, the investigator will inquire about the occurrence of AE/SAEs since the last visit. Events will be followed for outcome information until resolution or stabilization.

All unresolved adverse events should be followed by the investigator until the events are resolved, the subject is lost to follow-up, or the adverse event is otherwise explained. At the last scheduled visit, the investigator should instruct each subject to report any subsequent event(s) that the subject, or the subject's personal physician, believes might reasonably be related to participation in this study. The investigator should notify the study sponsor of any death or adverse event occurring at any time after a subject has discontinued or terminated study participation that may reasonably be related to this study.

8.4 Reporting Procedures – Notifying the IRB

8.4.1 Adverse Event Reporting

AEs are not expected due to participation in this minimal risk study. However, AE forms will be completed at each of the study assessments as well as any AEs reported during the weekly intervention sessions.

Study participants will be encouraged to contact study staff immediately should any AEs occur during study participation. Periodic adverse event reporting will include any AE that occurs while a participant is on the research protocol, regardless of whether it is considered related to study participation. The PI will submit as part of annual progress reports to the IRB a summary of monitoring that took place; cumulative adverse event data; assessments that were performed to evaluate external factors or relevant information that may have an impact on the safety of study participants or ethics of the research study; outcomes of procedural reviews conducted to ensure participant privacy and confidentiality; and final conclusions regarding changes to the anticipated risk-to-benefit ratio of study participants and recommendations related to continuing, changing, or terminating the study.

